## 7.6. Exploratory Efficacy Analyses

Details of the planned displays for the exploratory endpoints are provided in [Appendix 10: List of Data Displays](#) and will be based on GSK data standards and statistical principles.

### 7.6.1. Proportion of Subjects Who Have an Elevated Blood Eosinophil Level That Meets the Pre-Defined Threshold During the 32-Week Study Treatment Period.

#### 7.6.1.1. Endpoint / Variables

Subjects who have an elevated blood eosinophil level (2 x baseline value or baseline value + 2500 cells/ $\mu$ L) during the 32-week study treatment period will be identified from the central laboratory haematology results. Samples taken from the date of first dose of study medication up until the date of Visit 11 (Week 32) will be considered in the derivation. Baseline will be defined as in Section [5.2](#).

#### 7.6.1.2. Strategy for Intercurrent (Post-Randomization) Events

The treatment effect to be estimated (estimand) will be the ‘treatment policy’ effect of initial randomised treatment. A treatment policy strategy will be used for the intercurrent events of a) discontinuation of study medication and b) receipt of alternative HES medications. Subjects withdrawing from the study prematurely leading to missing blood assessments for blood eosinophil count will be included in the analysis as having an elevated blood eosinophil level that meets the pre-defined threshold.

#### 7.6.1.3. Statistical Analyses / Methods

Endpoint

 
Proportion of subjects who have an elevated blood eosinophil level during the 32-week study treatment period.
 

Model Specification

 
Cochran-Mantel-Haenszel test stratified by baseline OCS dose (0-<math>\leq</math>20mg/day and <math>></math>20mg/day prednisone or equivalent) and region.
 
A supplementary analysis using a logistic regression analysis adjusting for covariates of baseline OCS dose (continuous scale), region, and treatment will also be performed.
 

Model Results Presentation

 
Number of subjects analysed in each treatment group.
 
Number of subjects who have an elevated blood eosinophil level during the 32-week study treatment period.
 
Test statistic and p-value for association between treatment and endpoint from Cochran-Mantel-Haenszel test.
 
Odds ratio and 95% CI from logistic regression model.
 
p-value from logistic regression model.
 

Subgroup Analyses

 
No subgroup analyses will be performed on this endpoint.
 

Sensitivity and Supportive Statistical Analyses

 
No sensitivity/supportive analyses will be performed on this endpoint.
 

## 7.6.2. FEV1, FVC and FEV1/FVC ratio

### 7.6.2.1. Endpoint / Variables

- Change from baseline FEV1 at each visit.
- Change from baseline FVC at each visit.
- FEV1/FVC at each visit.

### 7.6.2.2. Strategy for Intercurrent (Post-Randomization) Events

The treatment effect to be estimated (estimand) will be the ‘treatment policy’ effect of initial randomised treatment. A treatment policy strategy will be used for the intercurrent events of a) discontinuation of study medication and b) receipt of alternative HES medications. Subjects with missing data will be assumed to be missing at random in the analysis.

### 7.6.2.3. Statistical Analyses / Methods

Summary statistics for FEV1, FVC and FEV1/FVC at each visit will be presented by treatment, including change from baseline values. A separate summary and analysis excluding any data from timepoints where the subject did not withhold short-acting bronchodilators for 6 hours or long-acting bronchodilators for 12 hours will be produced. No statistical analysis will be performed on FEV1/FVC.

Endpoint

 
Change from baseline in FEV1.
 
Change from baseline in FVC.
 

Model Specification

 
Repeated measures with missing data assumed to be missing at random. A mixed effects model will be fitted with the following specification: 
 
Visit, treatment and region included as fixed categorical effects.
 
Baseline FEV1 (or FVC as appropriate) and baseline OCS dose included as continuous fixed covariates.
 
Interaction terms for baseline-by-visit and treatment-by-visit.
 
The Kenward and Roger method (DDFM = KR) for approximating the denominator degrees of freedom to correct for bias in the estimated variance-covariance matrix.
 
REPEATED statement with TYPE=UN to specify an unstructured covariance structure for the R matrix.
 
 
 

 
The OBSMARGIN option on the LSMEANS statement in order to compute the adjusted geometric means with weights proportional to the input data set.
 

Model Results Presentation

 
Number analysed in each treatment group.
 
LS Mean (SE) and LS Mean Change from baseline (SE) in each treatment group.
 
Mean difference, 95% CI and p-value for mepolizumab vs placebo.
 

Subgroup Analyses

 
No subgroup analyses will be performed on this endpoint.
 

Sensitivity and Supportive Statistical Analyses

 
The analysis will be repeated excluding any data from timepoints where the subject did not withhold short-acting bronchodilators for 6 hours or long-acting bronchodilators for 12 hours.
 

### 7.6.3. Echocardiogram

Echocardiogram/MUGA scans at Screening and Week 32 will be summarised by treatment for the ITT population. No statistical analysis of this endpoint will be performed.

### 7.6.4. Change From Baseline in HES Symptom Severity Based on HES Daily Symptoms (HES-DS) at Week 32

#### 7.6.4.1. Endpoint / Variables

For each of the 6 symptom domains (muscle/joint pain, chills or sweats, abdominal pain or bloating, breathing symptoms, nasal or sinus symptoms and skin symptoms), the change from baseline symptom score at Week 32 will be defined using the mean of the 7 daily symptom scores up to and including the date of the Week 32 visit as the Week 32 assessment, and the mean of the 7 daily symptom scores up to but not including the date of first dose of study treatment as the baseline assessment. For each symptom domain, if any of the 7 daily symptom scores are missing for either the Week 32 time point or the baseline time point, the mean of the available daily symptom scores for the relevant symptom domain over the 7-day period will be used to calculate the change from baseline.

The change from baseline most bothersome symptom score at Week 32 will be derived using the mean domain scores at Week 32 and baseline for the up to 3 symptom domains identified by the subject as most bothersome at Week 0 (Visit 2).

#### 7.6.4.2. Strategy for Intercurrent (Post-Randomization) Events

The treatment effect to be estimated (estimand) will be the ‘treatment policy’ effect of initial randomised treatment. A treatment policy strategy will be used for the intercurrent events of a) discontinuation of study medication and b) receipt of alternative HES medications. Subjects with missing change from baseline symptom score or missing most bothersome symptom score at Week 32 will be included in the analysis with the largest (i.e. worst) value observed for any subject.

### 7.6.4.3. Statistical Analyses / Methods

Summary statistics for the most bothersome symptom score and the symptom score for each symptom domain at each week of treatment will be presented, including change from baseline values. Assessment windows for each week are defined in Section 16.3.1.

Endpoint

 
Change from baseline in most bothersome HES symptom severity score (HES-DS) at Week 32.
 
Change from baseline in HES symptom severity score (HES-DS) for each symptom at Week 32.
 

Model Specification

 
Wilcoxon Rank Sum test stratified by median baseline symptom severity (baseline symptom severity <math>\leq</math> median and baseline symptom severity <math>></math> median), baseline OCS dose (<math>0 \leq 20</math> mg/day and <math>>20</math> mg/day prednisone or equivalent) and region.
 

Model Results Presentation

 
Number analysed in each treatment group.
 
Median change from baseline at Week 32 in each treatment group.
 
p-value for difference between treatments from Wilcoxon Rank Sum test.
 

Subgroup Analyses

 
No subgroup analyses will be performed on this endpoint.
 

Sensitivity and Supportive Statistical Analyses

 
Repeated measures analysis including assessments at Week 4, 8, 12, 16, 20, 24, 28 and 32. In this analysis missing data will be assumed to be missing at random and will not be imputed with the largest i.e. worst value. A mixed effects model will be fitted with the following specification: 
 
Time point, treatment and region included as fixed categorical effects.
 
Baseline symptom severity and baseline OCS included as continuous fixed covariates.
 
Interaction terms for baseline-by-timepoint and treatment-by-time point interaction.
 
The Kenward and Roger method (DDFM = KR) for approximating the denominator degrees of freedom to correct for bias in the estimated variance-covariance matrix.
 
REPEATED statement with TYPE=UN to specify an unstructured covariance structure for the R matrix.
 
The OBSMARGIN option on the LSMEANS statement in order to compute the adjusted geometric means with weights proportional to the input data set.
 
 
 

### 7.6.5. Change from Baseline in BFI Total Score at Week 32

#### 7.6.5.1. Endpoint / Variables

The full BFI is completed every 7 days at home on the eDiary. The BFI total score will be calculated as the mean of the 9 item scores recorded for the weekly assessment, as long as at least 5 of the 9 item scores are complete. The change from baseline in BFI total

score at Week 32 will be calculated using the weekly assessment windows for Week 32 and baseline defined in Section 16.3.1.

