7.12.1. Brief Fatigue Inventory

The Brief Fatigue Inventory (BFI) is a tool developed for the rapid assessment of fatigue severity for use in both clinical screening and clinical trials [Mendoza, 1999]. The BFI has 9 items. The subject should rate their average and worst fatigue levels over the previous 24 hours using a numeric rating scale anchored with 0 (no fatigue/interference) and 10 (as bad as you can imagine/completely interferes) numeric rating scales. The subject will complete one item of the BFI daily and the full BFI every 7 days at home on the eDiary.

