**CONFIDENTIAL**

200622

Procedures	Pre-screen	Screen	Randomization	Double-blinded treatment period												Additional follow-up
Study treatment administration 			X		X	X	X	X	X	X	X					
Dispense/collect blinded OCS			X	X	X	X	X	X	X	X	X	X		X	X	
Interactive Response Technology (IRT)/electronic CRF (eCRF)/electronic Diary (eDiary)																
Register visit on IRT	X	X	X	X	X	X	X	X	X	X	X	X	X	X	X	X
Complete eCRF		X	X	X	X	X	X	X	X	X	X	X	X	X	X	X
Dispense (D) /collect (C) eDiary 		D										C		C for Visit 11	C	
Review eDiary			X	X	X	X	X	X	X	X	X	X		X	X	

EW: Early withdrawal

1. Pre-screen visit to obtain informed consent can occur on the same day as Visit 1, but informed consent must be obtained prior to starting Visit 1 procedures.
2. Parasitic screening is only required in countries with high-risk or for subjects who have visited high-risk countries in the past 6 months. Sites should use local laboratories.
3. Subject-completed assessments are done at the beginning of a visit.
4. Echocardiogram is performed to support CV assessment at screening and at the end of study treatment for all subjects. Echocardiogram at Visit 1 is required unless there is a documented result within the previous 6 months from Visit 1.
5. Findings during physical examination related to HES will be recorded in the HES Core Assessments/flare detail.
6. Height to be measured at screening only.
7. Vital sign measurements will include temperature, systolic and diastolic blood pressure and pulse rate.
8. During the treatment period, all laboratory samples (Protocol Table 4) should be obtained pre-dose.
9. Refer to protocol Section 6.4 for additional blood draw between the scheduled clinical visits for subjects who will administer blinded OCS.
10. Clinical chemistry will include analytes and liver chemistry monitoring.
11. Negative urine pregnancy test result must be confirmed prior to dosing in women of reproductive potential.
12. Lipoprotein (fasting) included in clinical chemistry. Subject must be in a fasting state. If the subject has not fasted, he/she may return to the clinic to collect this sample.
13. Urine tests are done using dipstick. If found abnormal, the urine sample will be sent to the central laboratory for further testing.
14. If test was performed within 3 months prior to randomization, testing at screening is not required.
15. F/P test is required if no documented results are available.

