### 16.3. Appendix 3: Assessment Windows

#### 16.3.1. Definition of Weekly Assessment Windows

Daily assessments of BFI item 3 and HES daily symptoms as well as weekly assessments of the full BFI will be assigned a single weekly analysis time point according to the table below.

Analysis Timepoint	Analysis Window		
	Beginning Timepoint	Ending Timepoint	Special Rules for Handling Overlapping Timepoints
Week 32	Week 32 (Visit 11) visit date – 6 days	Week 32 (Visit 11) visit date	
Week 31	Week 32 (Visit 11) visit date – 13 days	Week 32 (Visit 11) visit date – 7 days	If assessment falls into Week 31/Week 30/Week 29 and Week 28, assign assessment as Week 28. If assessment date is less than Week 28 (Visit 10) visit date, assign a relevant timepoint less than Week 28.
Week 30	Week 32 (Visit 11) visit date – 20 days	Week 32 (Visit 11) visit date – 14 days	
Week 29	Week 32 (Visit 11) visit date – 27 days	Week 32 (Visit 11) visit date – 21 days	
Week 28	Week 28 (Visit 10) visit date – 6 days	Week 28 (Visit 10) visit date	
Week 27	Week 28 (Visit 10) visit date – 13 days	Week 28 (Visit 10) visit date – 7 days	If assessment falls into Week 27/Week 26/Week 25 and Week 24, assign assessment as Week 24.
Week 26	Week 28 (Visit 10) visit date – 20 days	Week 28 (Visit 10) visit date – 14 days	
Week 25	Week 28 (Visit 10) visit date – 27 days	Week 28 (Visit 10) visit date – 21 days	If assessment date is less than Week 24 (Visit 9) visit date, assign a relevant timepoint less than Week 24.
Week 24	Week 24 (Visit 9) visit date – 6 days	Week 24 (Visit 9) visit date	
Week 23	Week 24 (Visit 9) visit date – 13 days	Week 24 (Visit 9) visit date – 7 days	If assessment falls into Week 23/Week 22/Week 21 and Week 20, assign assessment as Week 20.
Week 22	Week 24 (Visit 9) visit date – 20 days	Week 24 (Visit 9) visit date – 14 days	
Week 21	Week 24 (Visit 9) visit date – 27 days	Week 24 (Visit 9) visit date – 21 days	If assessment date is less than Week 20 (Visit 8) visit date, assign a relevant timepoint less than Week 20.
Week 20	Week 20 (Visit 8) visit date – 6 days	Week 20 (Visit 8) visit date	
Week 19	Week 20 (Visit 8) visit date – 13 days	Week 20 (Visit 8) visit date – 7 days	If assessment falls into Week 19/Week 18/Week 17 and Week 16, assign assessment as Week 16.
Week 18	Week 20 (Visit 8) visit date – 20 days	Week 20 (Visit 8) visit date – 14 days	

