### 16.4.2. Treatment Phases for BFI and HES-DS

Since the electronic diary is completed daily in the evening, BFI and HES-DS assessments will be classified as follows:

Study Phase	Definition
Pre-Treatment	Assessment date < Date of first dose of study treatment
On-Treatment	Date of first dose of study treatment ≤ Assessment date ≤ Date of last dose of study treatment + 28 days
Off-Treatment	Date of last dose of study treatment + 28 days < Assessment date ≤ Date of Week 32 visit /Study withdrawal date
Post-Treatment	Assessment date > Date of Week 32 visit

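### Exploratory BFI total at Week 32: a weekly entry due on the Visit 11 date may not be recordable, and the window rules would then score a study completer as worst case

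*SAP*

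**What the plan says.** Section numbers are those of the amended SAP of 18 June 2019.

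- **Frequency.** Protocol 7.12.1: "The subject will complete one item of the BFI daily and the full BFI every 7 days at home on the eDiary". SAP 7.6.5.1 repeats it: "The full BFI is completed every 7 days at home on the eDiary". Neither names the weekday on which the weekly form falls due.
- **Week 32 value.** SAP 7.6.5.1 ties it to the window table: the change in BFI total "score at Week 32 will be calculated using the weekly assessment windows for Week 32 and baseline defined in Section 16.3.1". In that table the Week 32 window starts at "Week 32 (Visit 11) visit date – 6 days" and ends on the visit date. The Week 31 window ends at "Week 32 (Visit 11) visit date – 7 days". Each weekly form is given one time point only.
- **Time of day.** SAP 16.4.2: "Since the electronic diary is completed daily in the evening". SAP 2.4 says that item 3 is recorded after 6pm.
- **Collection.** In the schedule of events (Protocol 7.1, SAP 16.2.1), the row "Dispense (D) /collect (C) eDiary" shows dispensing at screening and collection at Visit 11.
- **Missing value.** SAP 7.6.5.2 gives any subject without a Week 32 change the worst one seen in the trial. The rule is not limited to subjects who withdrew.
- **Supportive analysis.** SAP 7.6.5.3 adds a repeated measures model under missing at random, without that imputation.

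**The concern.** The BFI total has at most one entry per seven-day window and no fallback. If the form falls due on the Visit 11 date, it would be filled in that evening, possibly after the device has been handed back. The last recorded form is then seven days before the visit, one day outside the Week 32 window. The subject stayed in the study to Week 32, yet is ranked with the worst outcome.

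No other rule catches this case. The overlap rules in SAP 16.3.1 settle conflicts with earlier visits. The re-assignment rules in SAP 16.5.2 cover unscheduled and early withdrawal visits. The daily measures are not exposed in this way: item 3 and HES-DS use the mean of the days available (SAP 7.5.1 and 7.6.4.1), so they lose at most one day of seven.

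What is at stake is sensitivity in the main analysis of an exploratory endpoint, because tied worst ranks that carry no information about treatment would be added to both arms.

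**Working it through.** The plan states no figure for this endpoint, so there is none to reproduce. The check is date arithmetic.

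**1. Coverage of the window.** Take Visit 11 as day 0 and a strict 7-day cadence. The last due day is then k days before the visit, with k from 0 to 6.

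| Last due day | Window −6 to 0, visit evening recordable | Window −6 to 0, not recordable | Latest entry in −7 to 0, not recordable |
|---|---|---|---|
| k = 1 to 6 | entry at −k | entry at −k | entry at −k |
| k = 0 | entry at 0 | none (−7 is Week 31) | entry at −7 |
| Positions covered | 7 of 7 | 6 of 7 | 7 of 7 |

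If the visit evening is recordable, the extended range also covers 7 of 7. With k = 0 it holds entries at −7 and 0, the latest is day 0, and nothing changes.

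**2. Overlap with Week 28.** Visit 10 is at day 196 ± 7 and Visit 11 at day 224 ± 7. The shortest in-window gap is 217 − 203 = 14 days. An entry at −7 is therefore at least 7 days after Visit 10 and cannot fall in the Week 28 window.

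**3. Share affected.** The documents do not give it.

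- It is 0 if the visit-evening entry can be made, whatever the due day.
- It is 0 if due days never coincide with Visit 11.
- It could be nearly all if the entry cannot be made and the weekly form falls on the dosing weekday with visits on time, because 224 = 32 × 7.
- Illustration: if the entry can be made by nobody and due days are uniform over the week, it is 1/7 = 14.3%. If all randomised subjects complete, that is 80/7 = 11.4, or 120/7 = 17.1 at the maximum sample size.

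**4. Effect on the Wilcoxon comparison.** Let θ be the probability that a mepolizumab subject does better than a placebo subject, with ties counted as half. Let a fraction f of each arm, unrelated to outcome, take one shared worst value. The test is treated as unstratified.

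- Neither subject affected, probability (1−f)²: contributes θ.
- Only the placebo subject affected, f(1−f): contributes 1.
- Only the mepolizumab subject affected, f(1−f): contributes 0.
- Both affected, f²: contributes 0.5.

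Hence θ′ − 0.5 = (1−f)²θ + f(1−f) + f²/2 − 0.5 = (1−f)²(θ − 0.5).

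At f = 1/7 the factor is 36/49 = 0.735, a shrinkage of 13/49 = 26.5%. At f = 0 there is none.

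**The case against.** The strongest objection is that the premise is not in the documents. No section gives the visit hour, the hand-in time or a device lock, and a collection mark in a schedule names the visit, not the hour. Some of the text points the other way. The Week 32 window includes the Visit 11 date. Protocol 9.4.1 and SAP 7.5.1 count that date among the seven days for item 3. SAP 2.4 shows that the authors thought about evening entries: they removed the dosing date from baseline but kept the Visit 11 date at Week 32. SAP 16.4.2 also has a class for entries with "Assessment date > Date of Week 32 visit", although the flare and other efficacy tables carry the same row, so that is weak evidence.

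This objection stands as far as certainty goes. A reader might infer that compliant completers will be scored as failures, or that about one subject in seven will be. The documents support neither. The first needs a hand-in time and the device's rules on early or late completion. The second also needs due days spread evenly over the week.

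It is also fair that the endpoint is exploratory and that the repeated measures model avoids the imputation. That model is only supportive, however, and it would lack the same Week 32 values.

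The objection does not remove the gap. If the entry cannot be made, nothing in the SAP stops the worst-value rule from applying.

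**Conclusion.** The point holds as a conditional gap in the BFI total rules: minor, with low to medium confidence. It rests on two things that the documents leave open: whether a full BFI can be recorded on the evening of Visit 11, and on which day the weekly form falls due. The loss is zero if the answer to the first is yes. Under both unfavourable assumptions (no such entry, uniform due days) it is 1 in 7 and a shrinkage of about 26.5%.

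A reader might suspect bias towards one arm. Nothing in the mechanism depends on treatment; what it produces is dilution, with both medians moved towards worse. Nor does the point reach the testing hierarchy: BFI total is outside it, and item 3, which is in it, is protected by the available-days mean.

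**What to change.** For BFI total only, amend SAP 7.6.5.1 and 16.3.1, one line in each, before unblinding:

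- The Week 32 value is the latest full BFI dated from Visit 11 minus 7 days up to and including Visit 11.
- An entry at minus 7 counts as Week 32, and not also as Week 31, when no later one exists.
- Worst-value imputation applies only if no full BFI exists in that range.

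Leave the item 3 and HES-DS windows as they are; the item 3 window is set by Protocol 9.4.1.

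The change needs no new data and no further subjects. It does not depart from the protocol, because Protocol 9.4.5 leaves exploratory analysis details to the RAP. A subject on a strict 7-day cadence who can enter data on the Visit 11 evening keeps the same value.

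The cost is that a few Week 32 values are taken one day earlier than the present limit, and those entries leave the Week 31 summary. The repeated measures model does not use Week 31. A subject who could have completed the form on Visit 11 but did not would also be given the minus 7 value instead of the worst one.

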### 7.6.5.2. Strategy for Intercurrent (Post-Randomization) Events

The treatment effect to be estimated (estimand) will be the ‘treatment policy’ effect of initial randomised treatment. A treatment policy strategy will be used for the intercurrent events of a) discontinuation of study medication and b) receipt of alternative HES medications. Subjects with missing change from baseline symptom score at Week 32 will be included in the analysis with the largest (i.e. worst) value observed for any subject.

